# 4.3. Secondary Outcomes

- 1. To determine if the markers have any prognostic significance by the expression profile with tumour grade, stage and histology.
- 2. To determine if the markers could be used as tools to assess effects of treatment.

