# **STUDY SUMMARY**

STUDY TITLE	Adipocytokines and their relationship with		
	obesity and endometrial cancer		
SHORT TITLE	Adipocytokines in endometrial cancer		
STUDY DESIGN	exploratory biomarker study		
STUDY PARTICIPANTS	Study population - patients presenting to		
	Royal Surrey NHS Foundation Trust with		
	endometrial cancer, identified at the MDT		
	Control population - female patients		
	without endometrial cancer, referred for		
	benign condition.		
PLANNED SIZE OF SAMPLE	100-120		
FOLLOW UP DURATION	N/A		
PLANNED STUDY PERIOD	36-48 months		
RESEARCH QUESTION /AIM(S)	To investigate the relationship between		
	adipocytokine level in blood and tissue		
	(endometrial cancer tissue, adipose tissue		
	and lymph node) in patients with		
	endometrial cancer and co-relate with BMI		
	to identify peripheral biomarkers that can		
	be used as prognostic or diagnostic tools		

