Also, in an inflammatory environment, macrophages secrete potent proinflammatory cytokines such as TNF- $\alpha$  and IL-6, which are known to activate numerous transcription factors that regulate the expression of genes involved in immune responses, anti-apoptosis,

angiogenesis, and metastasis. The mechanisms of tumorigenesis are thought to be involved are free-radical production that cause DNA damage and impaired DNA repair.

Research have further suggested that systemic levels of insulin-like growth factor (IGF) is dysregulated in obesity either due to increased IGF production or by down-regulation of IGF binding protein (IGFBP) prodution. IGF 1 is a growth and proliferation promotor and has inhibitory effects on cell death and is a major contributor in many neoplastic transformation.

The above biomarkers are physiologically interrelated and are likely to reflect a more restricted number of underlying biological pathways. Possibly, they work in a synergistic capacity to modulate the risk of developing endometrial cancer. If specific patterns of cytokine expression were found to be predictive of adverse outcome, then the specific receptors may be targeted as a therapeutic option for endometrial cancer. No study so far has looked at all these markers together in the serum and tissue samples of the same endometrial cancer patients to give a more wholesome idea about their effect on tumour genesis, progression and outcome. Therefore, this study is designed to assess the prognostic significance of these six biomarkers in the blood and tissue of endometrial cancer patients and co-relating the levels with their BMI and tumour type, after adjusting for age, parity, smoking status, menopausal status, use of Hormone Replacement Therapy (HRT)/ hormonal contraception, and prevalence of diabetes and hypertension.

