### 5. STUDY DESIGN and METHODS of DATA COLLECTION AND DATA ANALYSIS

# 5.1. Study design

All patients being referred to the Royal Surrey NHS Foundation Trust with diagnosed uterine cancer will be given the research information leaflet and invited to participate as the study

population of the research. Female patients being referred to Royal Surrey NHS foundation Trust for benign conditions (specifically not endometrial cancer) will be invited to participate as the control population.

Initially, an invitation letter will be sent alongside the patients' clinic appointment letter to inform them of the study and give them time for preliminary consideration of the study. Patients will then be approached in the outpatients' clinics after the initial consultation by the clinician. Alternatively, patients may be approached over phone and information about the study given at that time. The call will be scheduled after the clinic appointment visit so that the patient will have received the Invitation Letter that is sent out with the initial Appointment Letter, allowing patients sufficient time to consider the study. Patients will be given a participant information leaflet detailing the study rationale, methodology and analysis in clinic or alternatively the leaflet will be sent by post/ email (in case of telephone consultations). Patients who agree to participate in the study will be asked to sign a consent form after explanation at a later appointment.

Demographic data will be collected at the same time to correlate various risk factors associated with the development of uterine cancer. The data collected will include age, parity, smoking status, menopausal status, medications used, use of Hormone Replacement Therapy (HRT)/ hormonal contraception, and prevalence of diabetes and hypertension. This data will be collected by:

- Taking a medical history from the patient in clinic
- Patients' medical notes

This data will be directly entered into an existing departmental database for Gynaecological oncology which is password protected and stored on NHS computers.

Study participants will then have 30mls (2 ½ tablespoons) of venous blood taken on the day of the surgery and control participants will also have 30mls of venous blood collection alongside their clinic appointment.

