Tissue samples from patients undergoing surgery will be collected as follows: For the study population, the PI will collect any fresh tissue (adipose tissue) directly from theatre before fixing as it is not needed for establishing diagnosis and the uterine cancer tissue and lymph node will be collected by the PI after histo-pathological examination from the histo-pathology department after the diagnosis is established. For the control population, if they are having uterine surgery, then the PI will collect some endometrial tissue after histo-pathological examination from the histo-pathology department after the diagnosis is established. All tissue processing will adhere to Human Tissue Authority (HTA) guidelines and will be performed at the Oncology laboratory at Leggett building at University of Surrey.

For study population only - the patients will have repeat blood tests (30mls of venous blood taken each time) on day 1 post-surgery and at their 3 or 6 months routine post-surgery follow up appointment. Control population will not have any repeat blood tests.

For the study population, women who are recommended chemotherapy, we will also ask consent to collect demographic data and baseline blood sample (30mls venous blood) at the time of consultation and after 3rd and 6th chemotherapy cycles to assess any changes in the markers that may correlate with progression or regression of disease.

We will also obtain archival serum samples and tissue blocks (of uterine cancer patients consented from a previous study for use during an appropriate ethics committee approved research) to help increase the number of recruitments for this study. Their demographic data with identification log will be made available to the PI only to assess for correlation between their data and the tissue diagnosis during analysis.

Timing of events including telephone contact events:

- 1. Send study Invitation Letter with Appointment Letter.
- 2. Clinic visit where patient is recruited/ phone call follow-up after clinic visit if the PI is not able to attend the clinic.
- 3. Enrolment of participant in study after consent.
- 4. Collection of blood and tissue sample as described above.

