### 8. ETHICAL AND REGULATORY CONSIDERATIONS

There is no direct benefit for the patients recruited into this study. They will be part of a research study which, in the future, may find ways of improving diagnosis of and survival from endometrial cancer.

Patients will not be disadvantaged in any way by participating in this research study – they will still receive standard clinical care for their condition.

Informed written consent will be taken from everyone who wishes to participate in the study. Written information leaflets will be given to the patients to read before they decide whether they wish to participate or not. Consent will be taken by doctors on the Gynaecological oncology team who have a clear and good understanding to this research and can take a valid informed consent.

All computers used to collect and save data will be stored in a securely locked room on NHS computer in NHS or University premises. Access to the computer will be password protected. Specific secure passwords will be needed to log onto these computers and this information will only be available to the researchers who are also part of the healthcare team. All computers will be encrypted to prevent access by any external source to the confidential information stored.

All personal information will be anonymised so that researchers except the PI will be blinded to this information. Information used for inference of prognostic outcomes will be based on generic data collected rather than individual information. At all times, the NHS Code of Confidentiality will be followed. Only the PI will have access to the 'key' to the patient identifiers. PI will be responsible for this.

All samples (blood and tissue) will then be transferred by the PI to the Leggett Building at University of Surrey for processing and storage following HTA regulations. The samples will be double boxed for transfer. The outside box will be an ice-box. The PI will personally transport the tissues by foot from the hospital to the Leggett building as they are very near geographically and it is a short 4 minutes walk.

Samples will be also be stored anonymised (in case of patients who give consent) in Leggett building, University of Surrey following all regulations by HTA) for use in future ethics approved research project. The patient will still be able to take part in this current study even if she does not consent to her data/ samples to be used in a future study.

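### Secondary outcome 1 reads prognostic significance from association with grade, stage and histology; no patient outcome is defined, and the survival models named in 5.5 do not fill the gap

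*Combined protocol and SAP*

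**What the plan says.** Section 4.3, item 1, sets the secondary outcome: "To determine if the markers have any prognostic significance by the expression profile with tumour grade, stage and histology". Section 1 describes the study as "designed to assess the prognostic significance of these six biomarkers in the blood and tissue of endometrial cancer patients". The Study Summary hopes for peripheral markers that can "be used as prognostic or diagnostic tools".

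On patient outcome the documents say little:

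- The Study Summary has "FOLLOW UP DURATION N/A".
- The data list in 5.1 begins "The data collected will include age, parity, smoking status, menopausal status, medications used" and goes on to hormone use, diabetes and hypertension. It has no item for recurrence, progression, death or vital status.
- Surgical cases give repeat blood "on day 1 post-surgery and at their 3 or 6 months routine post-surgery follow up appointment". That is their last planned contact.
- Women having chemotherapy give serial samples "to assess any changes in the markers that may correlate with progression or regression of disease". This belongs with secondary outcome 2 (treatment effect), and neither progression nor regression is defined as an endpoint.

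Section 5.5 assigns log-rank tests and a Cox model, adjusted for age, stage, grade and histology, to the correlation of markers with clinical characteristics. It gives no event, time origin or censoring rule. It sets P<0.05 as significant.

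**The concern.** A prognostic marker is one that carries information about what later happens to the patient. Item 1 relates the marker only to grade, stage and histology, which are fixed at diagnosis or surgery. An association with them shows that the marker tracks features the pathologist already reports. It does not show that the marker predicts recurrence or death, or that it adds to those features.

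The criterion can therefore mislead in two directions. A marker that only mirrors stage or grade can satisfy it. A marker that predicts outcome independently of all three features, which would be the useful new tool, has no route to satisfying it except chance.

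At stake is what the thesis and papers may claim. A statement that a marker is, or is not, prognostic would not follow from this comparison however the tests came out.

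**Working it through.** The plan gives no effect size, event count or power for this outcome, so there is no figure to reproduce. The argument rests on the text; the numbers only illustrate it.

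**1. The places that must agree**

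| Place | Role of stage, grade, histology | Patient outcome |
|---|---|---|
| Summary | none stated | follow-up not applicable |
| Section 1 | none stated beyond tumour type | prognostic purpose, no endpoint |
| 4.3 item 1 | the criterion | none |
| 5.5 | adjusters in a Cox model | methods need one; none given |

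The same three features are the yardstick in 4.3 and the nuisance variables in 5.5. Both cannot describe one analysis.

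**2. Chance rate for a marker unrelated to the three features**

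With three tests at 0.05, taken as independent: 1 − 0.95³ = 0.143. Outcome is not an input, so this rate is the same whatever the marker's hazard ratio.

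**3. Illustration of the criterion**

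Inputs from the documents: 30-60 cases including archived samples (7.3); P<0.05 (5.5). Assumed:

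- two-sided tests;
- stage in four levels (cumulative 0.65/0.75/0.92), grade in three (0.45/0.75), 20% non-endometrioid histology;
- latent correlation 0.4 among the three features;
- Spearman tests for stage and grade, Mann-Whitney for histology;
- a marker counted as flagged if any of the three P-values is below 0.05.

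There were 4,000 simulated studies per cell. The correlation shown is between the marker and each of the three features.

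| Cases | 0 | 0.3 | 0.4 | 0.5 |
|---|---|---|---|---|
| 30 | 14% | 49% | 74% | 90% |
| 60 | 14% | 77% | 94% | 99.6% |

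No outcome was simulated here. The non-zero columns stand for a marker with nothing to add beyond the features. The zero column stands for any marker unrelated to them, including a strongly prognostic one.

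**4. Sensitivity**

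- Correlation 0.2 with all three features: about 30% (30 cases) and 46-48% (60 cases).
- Correlation 0.3 with stage only: about 31% and 51%.
- A different model (30% advanced stage, marker shifted 0.5/0.8/1.0 SD by stage), significant for stage itself: 20/44/62% at 30 cases and 37/77/90% at 60. An unrelated marker was flagged for any feature in 13-15%.

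**5. What an outcome-based analysis could do**

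Assume 60 cases, stage hazard ratio 4, and Cox adjustment for stage only (400 simulated studies per setting). A redundant marker is flagged in about 5-6%. An independent marker with hazard ratio 2 per SD is flagged in about 60%, 76% and 96% with 12, 18 and 30 events.

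For a marker split at the median with hazard ratio 2, 80% power needs:

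- Schoenfeld: (1.960 + 0.842)² / (0.25 × (ln 2)²) = 7.849 / 0.1201 = 65.3, so 66 events.
- Freedman: 7.849 × ((2 + 1)/(2 − 1))² = 70.6, so 71 events.

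Both exceed the maximum of 60 cases. With 6, 12 or 18 events, power is 13%, 22% or 31%. The per-SD figures are higher because a hazard ratio of 2 per SD (variance 1) is a larger effect than 2 between halves (variance 0.25).

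**The case against.** The strongest reply is Section 5.5. A Cox model adjusted for age, stage, grade and histology is the right kind of analysis for independent prognostic value, and a redundant marker would not be favoured by it. That stands as a point about the method, and it means 4.3 cannot be read alone. It does not rescue the outcome. The model has no event, time origin or censoring rule, is tied to clinical characteristics, and sits beside a summary that gives follow-up as not applicable.

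A second reply is that the summary labels the study exploratory and that item 1 is one sentence of intent. This bears on severity. It does not turn association with stage into evidence about outcome.

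Four stronger readings are tempting and should be resisted:

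- *That redundant markers will be called prognostic and useful ones missed.* The plan gives no decision rule linking a P-value to the label. The any-of-three rule is an assumption made for the illustration, and the text shows only what the criterion permits.
- *That the criterion favours the redundant marker about sevenfold.* That ratio (0.996/0.14) comes from the most extreme cell. At 30 cases and correlation 0.3 it is 0.49/0.14 = 3.5, and weaker correlations give less. A prognostic marker partly correlated with stage would also be flagged more often than 14%.
- *That Section 8 rules out individual outcome data.* The sentence "Information used for inference of prognostic outcomes will be based on generic data collected rather than individual information" sits in a paragraph on anonymisation and recurs in 8.7 in the same context. It does not define how prognosis is judged.
- *That outcome data could not be obtained.* Section 3 mentions recurrence as motivation for monitoring treatment, and 5.1 uses an existing departmental database. The documents do not say that outcomes are unavailable; they define none.

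**Conclusion.** The point holds as an inconsistency with a consequence for inference. Section 4.3 item 1 makes association with grade, stage and histology the basis for prognostic significance. Section 1 and the summary promise prognostic findings, the summary gives no follow-up, and 5.5 names survival methods with nothing to run them on. A prognostic conclusion drawn under item 1 would be unsupported.

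This conclusion needs no simulation: a comparison that does not use outcome cannot respond to a marker's effect on outcome. The percentages rest on correlations and on stage, grade and histology distributions that the documents do not give. They show that the problem could be common at 30-60 cases, not how often it would occur in this study. The diagnostic aim, served by the case-control comparison in 4.2, is not in question.

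**What to change.** Preferred, since it needs no new data or patients:

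1. Reword 4.3 item 1 to: *To determine whether marker levels are associated with tumour grade, stage and histology.*
2. In 5.5, state that this is reported as clinicopathological association and that no prognostic conclusion will be drawn from it. For this outcome, replace the log-rank and Cox sentence with cross-sectional tests of marker level against stage, grade and histology.
3. In the Study Summary and Section 1, replace the prognostic claim with *candidate markers for later prognostic evaluation*. Keep the diagnostic aim in the summary.

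Alternatively, keep the word prognostic and the Cox model only for an explicitly exploratory analysis with a defined event, time origin and censoring rule. That analysis should test whether the marker adds to age, stage, grade and histology. The follow-up entry in the summary and the data list in 5.1 would then have to change to match. With at most 60 cases it could be informative only if events are frequent or effects large.

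The first route costs wording and a more modest stated claim. The second also costs outcome collection and follow-up.

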### 5. STUDY DESIGN and METHODS of DATA COLLECTION AND DATA ANALYSIS

# 5.1. Study design

All patients being referred to the Royal Surrey NHS Foundation Trust with diagnosed uterine cancer will be given the research information leaflet and invited to participate as the study

population of the research. Female patients being referred to Royal Surrey NHS foundation Trust for benign conditions (specifically not endometrial cancer) will be invited to participate as the control population.

Initially, an invitation letter will be sent alongside the patients' clinic appointment letter to inform them of the study and give them time for preliminary consideration of the study. Patients will then be approached in the outpatients' clinics after the initial consultation by the clinician. Alternatively, patients may be approached over phone and information about the study given at that time. The call will be scheduled after the clinic appointment visit so that the patient will have received the Invitation Letter that is sent out with the initial Appointment Letter, allowing patients sufficient time to consider the study. Patients will be given a participant information leaflet detailing the study rationale, methodology and analysis in clinic or alternatively the leaflet will be sent by post/ email (in case of telephone consultations). Patients who agree to participate in the study will be asked to sign a consent form after explanation at a later appointment.

Demographic data will be collected at the same time to correlate various risk factors associated with the development of uterine cancer. The data collected will include age, parity, smoking status, menopausal status, medications used, use of Hormone Replacement Therapy (HRT)/ hormonal contraception, and prevalence of diabetes and hypertension. This data will be collected by:

- Taking a medical history from the patient in clinic
- Patients' medical notes

This data will be directly entered into an existing departmental database for Gynaecological oncology which is password protected and stored on NHS computers.

Study participants will then have 30mls (2 ½ tablespoons) of venous blood taken on the day of the surgery and control participants will also have 30mls of venous blood collection alongside their clinic appointment.

Tissue samples from patients undergoing surgery will be collected as follows: For the study population, the PI will collect any fresh tissue (adipose tissue) directly from theatre before fixing as it is not needed for establishing diagnosis and the uterine cancer tissue and lymph node will be collected by the PI after histo-pathological examination from the histo-pathology department after the diagnosis is established. For the control population, if they are having uterine surgery, then the PI will collect some endometrial tissue after histo-pathological examination from the histo-pathology department after the diagnosis is established. All tissue processing will adhere to Human Tissue Authority (HTA) guidelines and will be performed at the Oncology laboratory at Leggett building at University of Surrey.

For study population only - the patients will have repeat blood tests (30mls of venous blood taken each time) on day 1 post-surgery and at their 3 or 6 months routine post-surgery follow up appointment. Control population will not have any repeat blood tests.

For the study population, women who are recommended chemotherapy, we will also ask consent to collect demographic data and baseline blood sample (30mls venous blood) at the time of consultation and after 3rd and 6th chemotherapy cycles to assess any changes in the markers that may correlate with progression or regression of disease.

We will also obtain archival serum samples and tissue blocks (of uterine cancer patients consented from a previous study for use during an appropriate ethics committee approved research) to help increase the number of recruitments for this study. Their demographic data with identification log will be made available to the PI only to assess for correlation between their data and the tissue diagnosis during analysis.

Timing of events including telephone contact events:

- 1. Send study Invitation Letter with Appointment Letter.
- 2. Clinic visit where patient is recruited/ phone call follow-up after clinic visit if the PI is not able to attend the clinic.
- 3. Enrolment of participant in study after consent.
- 4. Collection of blood and tissue sample as described above.

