# 4.2. Primary Outcomes

- To assess the circulating levels of adiponectin, leptin, tumour necrosis factor alpha (TNFα), interleukin 6 (IL-6), Insulin like growth factors 1 and 2 (IGF 1 and 2) in blood and at tissue level (endometrial tissue, adipose tissue, lymph node) from women with endometrial cancer (study population) and in the blood +/- endometrial tissue (control population) and to compare the results between the two groups.
- Additional tests on the samples collected looking at the cancer tissue
  microenvironment for infiltrating inflammatory cells +/- their secretions or other
  adipocytokines. We may also look at the tumour microbiome to look for any
  commensal bacteria or micro-organism and if available, to compare with tissue
  micro-environment and microbiome of normal endometrial tissue from control
  population.
- 3. To determine whether there is a correlation between these markers and obesity (classified by WHO category of BMI) after adjusting for confounding factors like age, parity, menopause, use of HRT/ hormonal contraception, smoking, diabetes and hypertension.

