#### 6. STUDY SETTING

Study patients will be recruited when attending a clinic in the department of Gynaecological Oncology at Royal Surrey NHS Foundation Trust. Private consultation rooms are available here for discussing the study, history taking and consenting.

Blood sample will be collected on the day of the surgery when they are in the theatres and then repeated on day 1 post-operative in gynaecology ward and at 3 or 6 months post-surgery follow-up in clinic.

Tissue samples will be obtained from the following areas:

- 1. Adipose tissue from the main theatres at Royal Surrey NHS Foundation Trust
- 2. Uterine cancer tissue and lymph node from the histopathology department after they have finished analysis.

For those women recruited undergoing chemotherapy, blood sample will be procured at initial consultation and after 3rd (with the blood test before the fourth cycle of chemotherapy) and 6th cycles of chemotherapy. This can be performed in the Department of Gynaecological Oncology at Royal Surrey NHS Foundation Trust.

All samples (blood and tissue) will then be transferred to the Leggett Building at University of Surrey for processing and storage following HTA regulations. The samples will be double boxed for transfer. The outside box will be an icebox. The PI will personally transport the tissues by foot from the hospital to the Leggett building as they are very near geographically and it is a short 4 minutes' walk.

Control patients will be recruited when they attend a clinic appointment at Royal Surrey NHS Foundation Trust for any benign condition. Blood sample will be collected during their clinic appointment after written consent. If they are having any uterine surgery, endometrial tissue will be collected after histopathological diagnosis from the histo-pathology department.

Samples will also be stored anonymised (in case of patients who give consent) in Leggett building, University of Surrey following all regulations by HTA) for use in ethics approved future research project.

Historical samples / tissue blocks stored in the oncology department in the Leggett building, University of Surrey, from a previous study will also be used if appropriate consent is in place.

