### 7.1. Inclusion criteria

- 1. Study population- Women diagnosed with endometrial cancer
- 2. Control population Women being seen in clinic for benign conditions
- 3. Age 18 or above
- 4. Of sound mind so they can give informed consent
- 5. Historical tissue sample/ blocks from previous cases in the oncology department in the Leggett building also be used if appropriate consent is in place.

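### Control endometrium has no histology rule, and menopausal and hormonal status are not applied to the tissue comparison, so a tumour-versus-control difference could partly reflect benign pathology or hormonal state

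*Combined protocol and SAP*

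**What the plan says.** Control endometrium enters two primary outcomes in section 4.2.

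- Outcome 1 measures the six markers in cases and, for controls, "in the blood +/- endometrial tissue (control population) and to compare the results between the two groups".
- Outcome 2 covers additional tests. It would compare tumour findings, if material is available, with the "micro-environment and microbiome of normal endometrial tissue from control" population.

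The source of the tissue is given twice. Section 5.1: "For the control population, if they are having uterine surgery, then the PI will collect some endometrial tissue after histo-pathological examination". Section 6: "If they are having any uterine surgery, endometrial tissue will be collected after histopathological diagnosis from the histo-pathology department".

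Eligibility of controls is broad. Section 5.1 invites women referred "for benign conditions (specifically not endometrial cancer) will be invited to participate as the control population". Section 7.1 asks for "Women being seen in clinic for benign conditions". The exclusions in section 7.2 are age under 18 and lack of consent.

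Section 5.1 collects menopausal status, medications and use of HRT or hormonal contraception. Section 5.5 gives the case-control comparison one general sentence with no covariates. The only adjustment set there (age, stage, grade and histology) belongs to a Cox model.

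**The concern.** A tumour-versus-control tissue contrast can be read as a cancer effect only if the control tissue does not itself differ for some other reason. Two such reasons are left open.

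- **Benign endometrial pathology.** Tissue donors are the controls who need uterine surgery, and nothing in the eligibility criteria or collection rule removes specimens with a benign abnormality.
- **Hormonal state.** Cases and tissue-giving controls may differ in menopausal status or hormone use. The protocol itself treats these as confounders for the BMI correlation (section 4.2, outcome 3) and, in section 1, when relating markers to BMI and tumour type. It does not carry them over to this contrast.

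At stake is the meaning of a difference in marker staining in outcome 1, or in infiltrating cells, their secretions or the microbiome in outcome 2.

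**Working it through.** **1. What the plan fixes.** The plan gives no number of control endometrial specimens, no effect size, no SD and no power calculation, so there is no stated figure for this contrast to reproduce. Section 7.3 gives 30-60 cases, equal controls and a total of 100-120, but not how many controls will have uterine surgery.

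**2. Sections side by side.**

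| Question | Where it would be settled | What is there |
|---|---|---|
| Must control histology be normal? | 4.2, 5.1, 6, 7.1, 7.2 | The word normal in outcome 2 only; no rule |
| Is control histology known? | 5.1, 6 | Yes, tissue is released after diagnosis |
| Is it a listed data item? | 5.1 | No |
| Are menopausal status and hormone use collected? | 5.1 | Yes |
| Is cycle phase a listed data item? | 5.1 | No |
| Are hormonal covariates applied to the tissue contrast? | 5.5 | No |

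The Cox adjustment set cannot fill the gap: tumour stage and grade do not exist for controls.

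**3. Systematic shift (inputs assumed).** Let a share f of control specimens be shifted by d SD because of benign pathology or hormonal state, with no cancer effect. The spurious mean difference is f × d. For f = 0.5: 0.5 × 0.5 = 0.25 SD, and 0.5 × 1.0 = 0.50 SD.

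Rejection rates were simulated for a two-sided Mann-Whitney test at 0.05 (normal data, 10,000 runs per cell). Section 5.5 names that test only for blood against tumour tissue and does not state sidedness, so both are assumptions here, as are the numbers of control specimens.

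| Cases / control specimens | f | d = 0.5 | d = 1.0 |
|---|---|---|---|
| 30 / 10 | 0 | 0.047 | 0.046 |
| 30 / 10 | 0.25 | 0.057 | 0.090 |
| 30 / 10 | 0.50 | 0.097 | 0.232 |
| 30 / 10 | 0.75 | 0.148 | 0.454 |
| 60 / 20 | 0 | 0.048 | 0.048 |
| 60 / 20 | 0.25 | 0.075 | 0.141 |
| 60 / 20 | 0.50 | 0.154 | 0.415 |
| 60 / 20 | 0.75 | 0.276 | 0.752 |

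At f = 0 there is no shift, so d has no effect. The other rates follow directly from the assumed one-directional shift. They show what would happen if such a shift exists, not that it does.

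**4. Cycle phase alone (inputs assumed).** Suppose half of 10-20 tissue donors are premenopausal (n = 5 to 10), each equally likely to be in either of two phases that differ by 1 SD. The control mean then varies around its mid-mix value with SD 0.5 × √(0.25/n):

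- n = 5: 0.5 × √0.05 = 0.11 SD
- n = 10: 0.5 × √0.025 = 0.08 SD

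The largest possible departure, with every premenopausal donor in one phase, is 0.5 × 0.5 × 1 = 0.25 SD. If surgery dates fall without regard to cycle, phase is therefore mainly noise. The possible systematic part lies in menopausal status, hormone use and benign pathology.

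**The case against.** The strongest reply is that the plan's silence is being read as a rule. Control tissue is released only after histopathological diagnosis, and the wording of outcome 2 can be taken as a selection condition: use control tissue that is normal, where there is any. Outcome 1 makes no claim of normality and treats control tissue as optional. Menopausal status and hormone use are already collected, the data list is open-ended, the study is exploratory, and using tissue from clinically indicated surgery spares controls any extra procedure (section 8.1).

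Much of this stands. A reader might infer that tissue is used whatever the pathology report shows; no section says so. A reader might also infer a bias of 0.5 to 1.0 SD from cycle phase. The 0.5 SD figure is the distance between two extreme sets when half the donors are premenopausal, and 1.0 SD needs every donor to be premenopausal and in one phase; neither is an expected bias. Nor do the documents support calling the tissue results uninterpretable as a whole: phase does not apply to postmenopausal donors, and the share of donors with endometrial pathology is not given. Taking tissue from surgical controls is a feasibility constraint, not an error.

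What the reply does not supply is a rule. Even if normal is a selection condition, no section says which reported histology meets it, and nothing in section 5.5 applies the hormonal covariates to this contrast.

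**Conclusion.** The point holds in a limited form. Followed as written, the plan allows the tumour-versus-control tissue comparison to mix cancer with benign endometrial pathology or hormonal state, because control histology is neither constrained nor listed for recording and the hormonal data are not used in this contrast. The label normal is confined to the optional comparison in outcome 2, but outcome 1 draws on the same control tissue.

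Size and direction cannot be derived from the documents; the figures above rest on assumed shares, shifts and specimen numbers. Random cycle phase adds roughly 0.08 to 0.11 SD of noise on the stated assumptions. The blood comparison does not depend on uterine surgery and is unaffected. This is an inexpensive improvement to an exploratory comparison, not a flaw in the study as a whole.

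**What to change.** - **Section 5.1:** for each control tissue, copy the endometrial histology, and the phase where reported, from the existing pathology report into the study data.
- **Section 4.2:** limit the normal comparator to specimens reported as normal or atrophic. Report other benign control tissue separately as non-malignant.
- **Section 5.5:** stratify or adjust the tumour-versus-control tissue comparison by menopausal status and hormone use, both already collected. Show phase descriptively only, since a split of the premenopausal specimens by phase may leave very few in each group.

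This needs no new visit, sample or procedure: only items taken from a report that exists when the tissue is released, and edits to three sections. The downside is a smaller normal-tissue set and less precision in an exploratory comparison.
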